9.0 Study Population

Our study population will be adults with type 1 diabetes between ages 18 and 65 years who have a duration of at least 2 years and who have awareness of hypoglycemia according to the Cox questionnaire (11).

9.1 Inclusion Criteria:

- Type 1 diabetes diagnosed on clinical grounds (history of DKA, use of insulin within 6 months of diagnosis)
- Diabetes duration < 30 years (impaired awareness of hypoglycemia increases with duration so it will be more likely that shorter duration participants will have hypoglycemia awareness) but > 2 years (to ensure that they have lost hypoglycemia induced glucagon secretion as is typical in patients who develop impaired awareness of hypoglycemia)
- Age 18 – 65 years
- Subject reported hemoglobin A1c between 6.8 – 9.0% (range selected to reduce the risk of hypoglycemia and uncontrolled diabetes in the weeks before the study, both of which may affect the responses to hypoglycemia)
 - For subjects on low glucose suspend or closed loop pumps systems A1c can be < 6.8% if a 30 day download of their pump shows that they have had no episodes of hypoglycemia with a glucose < 60 mg/dL for more than 20 min.
- Awareness of hypoglycemia or indeterminate as verified by Cox questionnaire

9.2 Exclusion Criteria:

- History of stroke, seizures (other than those related to hypoglycemia), arrhythmias, active cardiac disease
- History of hypertension or blood pressure > 140/95 mm Hg at screening visit
- Pregnancy or plan to become pregnant during the study period
- Health related limitations in exercise (including but not limited to: angina, uncontrolled asthma, peripheral arterial disease)
- Unwillingness to avoid exercise during the 7 days before each part of the study
- Sedentary life style; defined as less than 60 minutes of moderate exercise per week
- Concomitant medical problems that may prevent the participant from successfully completing the protocol
- Smoking as defined by 2 or more tobacco cigarettes a week
- Daily use of opioids or an opioid antagonist or use in the past two weeks
- History of substance abuse
- Unwillingness to wear a continuous glucose monitor for one week before and one week after each part of the study
- Evidence of autonomic neuropathy; defined as:
 - Early satiety or orthostatic dizziness in the presence of, at least one during the screening visit:
 - Resting heart rate greater than 100
 - Systolic blood pressure fall of greater than 10 mm/Hg when moving from a supine to upright position with no change in pulse

PROTOCOL TITLE: Hypoglycemia after exercise in type 1 diabetes: Intranasal naloxone as a novel therapy to preserve hypoglycemia counterregulation

VERSION 8 – December 7, 2018

9.3 Screening:

Once the Informed Consent Form and HIPAA authorization has been signed, using a combination of participant self-report and medical record review, research staff will confirm each inclusion and exclusion criteria for eligibility.

10.0 Vulnerable Populations

10.1 Vulnerable Populations:

- Children
- Pregnant women/Fetuses/Neonates
- Prisoners
- Adults lacking capacity to consent and/or adults with diminished capacity to consent, including, but not limited to, those with acute medical conditions, psychiatric disorders, neurologic disorders, developmental disorders, and behavioral disorders
- Non-English speakers
- Those unable to read (illiterate)
- Employees of the researcher
- Students of the researcher
- None of the above

10.2 Additional Safeguards:

Not applicable. Vulnerable populations will not be included in this study.

11.0 Local Number of Participants

11.1 Local Number of Participants to be Consented:

Approximately 30 participants will be enrolled to ensure adequate numbers given possibility for screen failure or loss-to-follow up. Power analysis suggests that 25 participants will be necessary.

12.0 Local Recruitment Methods

12.1 Recruitment Process:

Participants will be directly recruited from the Diabetes and Endocrinology Clinics at M Health. Flyers will be posted at approved locations only with contact information so that interested candidates can call research staff. Flyers with information about the study will also be shared with endocrinologists in the community that they can give their patients about the study. If they are interested, they will directly contact study staff.

In addition, study information including contact information will be posted on ClinicalTrials.gov, at the Clinics and Surgery Center using approved recruitment cards, and on social media sites, including but not limited to blogs aimed towards people with Type 1 diabetes, Facebook, and Twitter. In addition, information may be posted on listservs, departmental websites, and in national and local newsletters, and distributed at community events.

PROTOCOL TITLE: Hypoglycemia after exercise in type 1 diabetes: Intranasal naloxone as a novel therapy to preserve hypoglycemia counterregulation

VERSION 8 – December 7, 2018

Participants in previous studies, who have given permission to be contact, will be called/mailed about the study and asked to consider enrollment. Only participants who have given permission for a direct telephone call will be called, all others will have the letter sent through the post office or electronic mail.

12.2 Source of Participants:

Participants could come from a variety of sources including self-selection from the public population at clinics where flyers have been posted and from medical record review of the patient population.

12.3 Identification of Potential Participants:

Participants could self-identify in response to recruitment advertisements and contact the research staff; at that point, research staff will verbally confirm basic eligibility and schedule a screening visit.

Research staff will also identify potential participants by reviewing medical records of affiliated study endocrinologists. Working with clinic staff, research clinicians will speak with their patients or a letter will be sent to explain the study and provide coordinator contact information. Study health care professionals will also speak to patients if, during the course of a standard-of-care visit, it becomes evident that they might be eligible and/or interested in research. Opt-out status will be reviewed prior to patient contact.

12.4 Recruitment Materials:

Recruitment materials, as submitted to and approved by the IRB include the following:

- Phone script
- Email or letter for former participants matching eligibility
- Letter from affiliated endocrinologist
- Recruitment card for the Clinics and Surgery Center
- Flyer
- Newsletter ad
- Social media guide, ads
- Short study descriptions for newsletters, listservs, etc.

12.5 Payment:

Each participant will be given reimbursements totaling \$675 for completing the entire study. This is broken down as follows:

- Screening Visit: \$25
- Part 1, Day 1: \$150
- Part 1, Day 2: \$150
- Part 2, Day 1: \$150
- Part 2, Day 2: \$200

PROTOCOL TITLE: Hypoglycemia after exercise in type 1 diabetes: Intranasal naloxone as a novel therapy to preserve hypoglycemia counterregulation

VERSION 8 – December 7, 2018

Compensation will be paid at the completion of each study visit. Compensation will be in the form of a check-request through the University of Minnesota which will be mailed to the participant's house or the Greenphire ClinCard debit card system.

13.0 Withdrawal of Participants

13.1 Withdrawal Circumstances:

Participants will be withdrawn without their consent if at any point following enrollment they develop any of the exclusion criteria.

13.2 Withdrawal Procedures:

No additional data will be collected from a participant who withdraws from the study. Because this is a paired study, withdrawn participants will be replaced with a new participant. Participants recruited to replace a withdrawn participant will be newly randomized and will not be a direct one-to-one replacement following the same treatment sequence.

13.3 Termination Procedures:

Any data collected on early-terminators will still be used, up to the point at which they formally withdrew consent. Baseline data from both completers and non-completers will be used to understand intervention effect and to better design future studies.

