Participants will be contacted at 1 week post final study procedure for adverse event assessment. This can be done by either telephone or email.

PROTOCOL TITLE: Hypoglycemia after exercise in type 1 diabetes: Intranasal naloxone as a novel therapy to preserve hypoglycemia counterregulation

VERSION 8 – December 7, 2018

	Screening	-6 to -1 days Part 1 Day 1	Part 1 Day 1		Part 1 Day 2	+1 to +7 days Part 1 Day 2	7 Week Washout Period	CGM-Only -7 Days before Part 2	-6 to -1 days Part 2 Day 1	Part 2 Day 1		Part 2 Day 2	+1 to +7 days Part 2 Day 2
			AM	PM						AM	PM		
Consent	X												
A1c	X										X		
VO ₂ peak/bike	X												
Education	X												
Urine Pregnancy Test	X		X								X		
Apply CGM	X								X				
Wear CGM		X	X	X	X	X				X	X	X	X
Home blood sugar monitoring		X				X				X			X
Randomization			X										
Download glucose meter/pump			X								X		
Exercise			X	X							X	X	
IV Infusion (insulin, glucose, potassium)			X	X	X						X	X	X
Naloxone/saline			X ¹	X ¹							X ¹	X ¹	
Blood collection: naloxone concentrations (only collected during active study drug)			X ²	X ²							X ²	X ²	
Blood collection: hormones (epinephrine, norepinephrine, glucagon, cortisol)					X ⁶								X ⁶
Glucose measurement			X ⁵	X ⁵	X ⁵						X ⁵	X ⁵	X ⁵
Blood Pressure	X												
Heart Rate			X ³	X ³							X ³	X ³	
VO ₂			X ⁴	X ⁴							X ⁴	X ⁴	
Questionnaires	X				X ⁷								X ⁷
Usual Activities							X						
Snack, if necessary			X	X	X						X	X	X
Meal				X	X						X	X	

¹ Naloxone/saline 4.0mg administered twice, time zero and +30 minutes

² Serum collection for naloxone at time points every 20-40 minutes

³ Heart rate collected continuously

⁴ VO₂ collected every 15 minutes

⁵ Collected from IV, resulted on bedside Analox machine

⁶ Serum collection: hormones

⁷ Questionnaires every 15 minutes

PROTOCOL TITLE: Hypoglycemia after exercise in type 1 diabetes: Intranasal naloxone as a novel therapy to preserve hypoglycemia counterregulation

VERSION 8 – December 7, 2018

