Specific safety data to be monitored includes those associated with naloxone administration and hypoglycemia. Participants will be continuously monitored during the administration of the naloxone/placebo by study personnel. At each study visit following consent, participants will be asked about their health since the last time they were seen by the study staff.

- Those specifically related to naloxone: musculoskeletal pain, headache, nasal symptoms, blood pressure, and other cardiac events.
- Glucose levels: if at any point during Part 1 or Part 2, glucose monitoring becomes impossible because of technical failure or other issue or if the MD/PA present suspects an immediate concern, the study will be immediately halted and blood sugar given to participant.

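### Section 13.2 has no safety exception, so a participant withdrawn by the investigators under 13.1 has no stated adverse event follow-up afterwards

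*Combined protocol and SAP*

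**What the plan says.** Section 13.1 gives one circumstance for withdrawal, and it is initiated by the investigators: "Participants will be withdrawn without their consent if at any point following enrollment they develop any of the exclusion criteria".

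Section 13.2 sets the procedure: "No additional data will be collected from a participant who withdraws from the study". The next sentence deals with replacement: "Because this is a paired study, withdrawn participants will be replaced with a new participant". Section 13.3 covers data already in hand: "Any data collected on early-terminators will still be used, up to the point at which they formally withdrew consent".

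The exclusion list in 9.2 includes "History of stroke, seizures (other than those related to hypoglycemia), arrhythmias, active cardiac disease", and also pregnancy.

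For safety, 5.3 plans a single closing contact: "Participants will be contacted at 1 week post final study procedure for adverse event assessment". Section 18.2 adds that participants are asked about their health at each study visit. It names among the specific safety data "Those specifically related to naloxone: musculoskeletal pain, headache, nasal symptoms, blood pressure, and other cardiac events". Section 1.1 makes tolerability a secondary aim.

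**The concern.** A rule that stops all data collection is normal when a participant revokes consent. It is a poor rule when the investigators remove a participant because of a medical event, since the reason for stopping is then itself safety information. Consent has not been revoked, the participant may be willing to answer a call, and how the event ended is what a tolerability assessment needs.

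At stake is the completeness of the safety record for a small group selected by outcome: people with a new cardiac condition after exercise and study drug, or a pregnancy discovered after exposure. Section 14.1 lists heart attack among the rare exercise risks, and 14.2 says that the effect of naloxone in human pregnancy is unknown. Later information on these participants would be informative, and no section provides for it.

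**Working it through.** No figure in the plan bears on this point, so the check is a comparison of sections.

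**1. Does 13.2 reach participants withdrawn under 13.1?** Section 13.1 describes only involuntary withdrawal. Section 13.2 follows it as the procedure, and its second sentence refers to participants who have been withdrawn. If the first sentence covered voluntary departure only, the protocol would contain no data rule for the one type of withdrawal that 13.1 describes. The natural reading is that 13.2 covers both.

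**2. Which conditions trigger 13.1 and also matter for safety?**

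| Condition in 9.2 | Can it arise after enrollment? | Link to the safety plan |
|---|---|---|
| Arrhythmia, active cardiac disease | Yes | Cardiac events are named in 18.2 |
| Pregnancy | Yes; the schedule of events repeats the urine test at Part 2 | Unknown human effect, per 14.2 |
| Stroke | Yes | Not named in 18.2 |
| Seizure not related to hypoglycemia | Yes | Not named in 18.2 |
| Seizure related to hypoglycemia | Exempt from the criterion | No withdrawal follows |
| Blood pressure above 140/95 mm Hg | The limit is tied to the screening visit | A later high reading does not clearly trigger withdrawal |

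New cardiac conditions, and pregnancy after exposure, are the clear cases.

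**3. What is still captured?** The triggering event. Under 18.2 the PI assesses it, and the DSMB is told of all adverse and serious adverse events within 48 hours. If a part was stopped early and an adverse event was reported, the DSMB reviews that participant's data within two weeks.

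**4. What is lost under 13.2 as written?** The plan has two stated routes for asking participants about events away from the unit: the health question at each later visit (18.2) and the closing contact (5.3). A withdrawn participant has no later visits, and 13.2 removes the contact. Someone withdrawn during the washout of about seven weeks would therefore have neither. No section says that the contact, or the recording of an event's outcome, survives withdrawal. Referral to a physician in 24.1 is care, not data collection.

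**5. How many people?** The documents do not say. The plan enrolls about 30 to obtain 25 completers (24.1) or 28 (16.2), a margin of 30 − 25 = 5 or 30 − 28 = 2 for non-completion of every kind. That margin is a planning allowance, not a forecast, and withdrawals under 13.1 would be only part of it.

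**The case against.** The strongest reply is that safety oversight does not end. The event that leads to withdrawal is recorded, assessed and sent to the DSMB within 48 hours, and the DSMB also reviews early stops and adverse events after 5, 10 and 15 randomizations and at the final one. This stands. A reader might infer that safety information stops altogether for the most seriously affected participants, or that the DSMB receives a flattering record. The documents do not support either. Only what follows the triggering event is missing.

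The second reply is that the text is ambiguous. Section 13.2 speaks of a participant who *withdraws*, whereas 13.1 speaks of participants being withdrawn. Section 5.3 does not limit the contact to completers, and the last procedure actually performed could count as the final one. That reading is available, but it leaves 13.2 silent on the only withdrawal that 13.1 defines, so the wording needs repair either way.

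The third reply is that a reader might extend the point to seizures and raised blood pressure in general. That goes too far. Seizures related to hypoglycemia are exempt from the exclusion criterion, and seizure is not named in 18.2. The blood pressure criterion reads "History of hypertension or blood pressure > 140/95 mm Hg at screening visit", so at most a newly established history of hypertension would plausibly lead to withdrawal.

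**Conclusion.** The point holds in a limited form. Sections 13.1 and 13.2, read together, stop data collection for participants whom the investigators withdraw, with no safety exception. This sits badly with the adverse event contact in 5.3 and with the tolerability aim. The loss is the outcome of the triggering event, later adverse events and the closing contact, for a few participants at most. The conclusion assumes that 13.2 applies to participants withdrawn under 13.1, which is the natural but not the only reading.

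Two stronger inferences should be resisted. First, 13.2 and 13.3 do not contradict each other: one governs new collection and the other governs use of data already collected, and both can be followed. Second, a reader might size the problem as a change in the event rate, since one participant in 25 to 30 is 1/30 = 3.3% to 1/25 = 4.0%. That would measure an unreported first event. Here the first event is reported, so the participant already counts as having had one, and the proportion with any event does not change. The plan sets no tolerability rate or bound against which to measure the loss.

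Nothing here affects the sample size or the primary analyses of symptom scores and epinephrine. It is an inexpensive improvement to a stated rule.

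**What to change.** Amend 13.2 to separate the two cases:

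- Withdrawal of consent, and only that, ends data collection.
- For a participant withdrawn under 13.1, study procedures stop. With the participant's agreement, the adverse event contact in 5.3 still takes place, counted as one week from that participant's last study procedure, and the outcome of any adverse event still open is recorded.

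Add a cross-reference in 5.3 so that the contact visibly applies to withdrawn participants. State how long open events are tracked, so that the duty is not open-ended, and whether a pregnancy after exposure falls under the same rule.

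The cost is a wording change and a brief phone or email contact for a few participants, with a further contact where an event is still open. The change concerns data collection only and does not alter clinical management.

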14.0 Risks to Participants

14.1 Foreseeable Risks:

Naloxone risks: Potential risks include increased blood pressure, musculoskeletal pain, headache, nasal dryness, nasal edema, nasal congestion, and nasal inflammation. Precipitated withdrawal can occur in those using opioids in the previous 24 hours. Participants will be questioned about opioid use before naloxone/placebo administration.

Bike Ride risks: Discomfort might be felt in body and mind from doing vigorous exercise. There is also risk of injury during exercise testing. These risks are rare and range from minor injuries such as a pulled muscle or sprained ankle to severe injuries such as a heart attack or even sudden death. The exercise test personnel will be monitoring participants every minute of the test to minimize these risks. A study physician or physician's assistant and a study nurse will also be in the room monitoring the subject during the exercise study and prepared to stop the study and administer care should a medical problem develop.

Hypoglycemia risks: Sweating, shakiness, confusion, and feeling “low”. Glucose levels will be monitored throughout Part 1 and Part 2 both days and the study will be stopped if participant's levels cannot be monitored due to technical malfunction or study MD/PA feels that it is no longer safe for the participant to continue. Glucose will be immediately be given to normalize the participant's levels.

PROTOCOL TITLE: Hypoglycemia after exercise in type 1 diabetes: Intranasal naloxone as a novel therapy to preserve hypoglycemia counterregulation

VERSION 8 – December 7, 2018

Blood draw risks: The risks associated with the blood draw include minimal discomfort, and/or bruising. Fainting is possible but unlikely. In very rare cases, a small blood clot can form at the site of the needle insertion. The main inconvenience is the time it will require for the blood to be drawn. The risks of the intravenous line are similar to a blood draw but because it is kept in the vein for a longer period of time (8 hours for Day 1, 4 hours for Day 2), the risk of bruising and discomfort are slightly higher. There will be two intravenous lines placed, one in each arm.

General participation risks: There is always the risk for a breach of confidentiality during the course of any research study.

14.2 Reproduction Risks:

Naloxone is a Schedule C drug, thus its use is not recommended in pregnant women. Animal studies have shown no adverse effect on the fetus but there are no adequate and well-controlled studies in humans so the effect on the human effect is currently unknown. It is also not known if naloxone is excreted in breast milk. Currently pregnant women nor those who are planning on becoming pregnant while enrolled will be excluded.

14.3 Risks to Others:

Not applicable.

15.0 Potential Benefits to Participants

15.1 Potential Benefits:

The only direct benefit to individual participants is a possible better awareness of hypoglycemia symptoms.

16.0 Data Management

16.1 Data Analysis Plan:

All randomized subjects who have complete outcome data for one or both of parts 1 and 2 will be included in the analysis. The Aim 1 primary outcome is difference in symptom scores collected during hypoglycemia on day 2 following the intranasal naloxone vs intranasal saline intervention on day one. The Aim 2 primary outcome will be the peak epinephrine during the hypoglycemic clamp on day 2 of each part, thus each participant will have two observations: one from their naloxone experiment and one from their saline experiment. The statistician will fit a general linear mixed model with fixed effects for treatment (Naloxone vs. saline), treatment order (Naloxone first vs. saline first), and period (Part 1 vs. Part 2) and a random effect for participant. The level of significance will be set at $p < 0.05$.

The study has been confidently designed, with a washout period of 7+ weeks between Parts 1 and 2, to ensure minimization of the possibility of a treatment effect from Part 1 that lingers into Part 2. Summary statistics will be used to examine whether measures of metabolic conditions showed clinically meaningful differences between naltrexone studies and saline studies. If there are, then the treatment comparison will be repeated using the same linear mixed model but with additional

PROTOCOL TITLE: Hypoglycemia after exercise in type 1 diabetes: Intranasal naloxone as a novel therapy to preserve hypoglycemia counterregulation

VERSION 8 – December 7, 2018

adjustment for the metabolic parameters of concern; this will be done separately for epinephrine and symptoms scores.

Secondary outcomes will be analyzed similarly, using models appropriate for the scale of the outcome (e.g., linear models, logistic models, binomial models).

Data analysis will also consider adjustment for important baseline characteristics, such as age and sex. Diagnostics will be examined to assess model assumptions. Baseline characteristics of those who do complete vs. those who do not complete both parts will be examined and used to inform interpretation of the treatment effect.

16.2 Power Analysis:

The primary outcome variable for Aim 1 will be the difference, naloxone vs. saline, in symptom scores collected using a standard questionnaire during the hypoglycemic clamp on Day 2, after administration of intranasal treatment during exercise on Day 1. The primary outcome variable for Aim 2 will be the difference, naloxone vs. saline, in peak epinephrine levels measured during the hypoglycemic clamp on Day 2, after administration of treatment during exercise on Day 1. In a previous study done with naltrexone (an opioid antagonist that can be given orally), the standard deviation of the differences in symptoms scores collected during hypoglycemia after participants were treated with drug vs. saline was 12.9 points (12). In the preliminary study with naloxone, symptom scores were found to be about 50% greater during hypoglycemia done on Day 2 following administration of intranasal naloxone vs. saline during hypoglycemia on Day 1 (with numerical differences ranging from 7 to 21). Based on these data, it is calculated that the necessary sample size of 25 completers to have 80% power to detect a difference of 7.53 points in symptom scores between those treated with intranasal naloxone vs. saline during exercise on day 1 with $p < 0.05$. Analysis of the data published in Milman et al (1), suggests that at least 15 subjects must complete the study for the power to detect a mean paired difference in hypoglycemia induced epinephrine secretion on Day 1 between those treated with intranasal naloxone vs. saline during exercise on day 1. Therefore, the plan is to enroll 30 subjects to ensure that we complete studies in the 28 subjects we need to address the first aim.

16.3 Data Integrity:

The PI will periodically review data for completeness and to ensure that all procedures are being followed as detailed in the protocol. The assigned Regulatory Specialist will also perform periodic quality assurance monitoring at any point requested by the PI.

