PROTOCOL TITLE: Hypoglycemia after exercise in type 1 diabetes: Intranasal naloxone as a novel therapy to preserve hypoglycemia counterregulation

VERSION 8 – December 7, 2018

ABBREVIATIONS/DEFINITIONS

- DSMB: Data and Safety Monitoring Board
- DSMP: Data and Safety Monitoring Plan
- Euglycemia: normal blood glucose concentration (60-100 mg/dL)
- Hypoglycemia: low blood glucose (<60 mg/dL)

PROTOCOL TITLE: Hypoglycemia after exercise in type 1 diabetes: Intranasal naloxone as a novel therapy to preserve hypoglycemia counterregulation

VERSION 8 – December 7, 2018

STUDY SUMMARY

Study Title	Hypoglycemia after exercise in type 1 diabetes: Intranasal naloxone as a novel therapy to preserve hypoglycemia counterregulation
Study Design	Randomized, placebo-controlled, crossover design
Primary Objective	Determine if intranasal administration of naloxone during exercise will be a novel approach to preserve the counterregulatory response to hypoglycemia experienced the next day in individuals with type 1 diabetes
Secondary Objective(s)	Pharmacokinetics and pharmacodynamics of naloxone using a population modeling design to explore dosing for future studies
Research Intervention(s)/ Investigational Agents	Naloxone
IND/IDE #	134687 (exempt)
Study Population	Individuals with Type 1 diabetes
Sample Size (number of participants)	Approximately 30
Study Duration for Individual Participants	Up to 15 weeks

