3.0 Study Endpoints/Events/Outcomes

3.1 Primary Endpoint/Event/Outcome:

The primary outcome variable for Aim 1 will be the difference, naloxone vs. saline, in symptom scores collected using a standard questionnaire during the hypoglycemic clamp on Day 2, after administration of intranasal treatment during exercise on Day 1.

The primary outcome variable for Aim 2 will be the difference, naloxone vs. saline, in peak epinephrine levels measured during the hypoglycemic clamp on Day 2, after administration of treatment during exercise on Day 1.

3.2 Secondary Endpoint(s)/Event(s)/Outcome(s):

Secondary endpoints will include:

- Glucose levels will be measured by continuous glucose monitor and home blood glucose monitoring during the 7 days after each experiment with specific levels of interest of > 54 mg/dL, > 54 mg/dL - < 70 mg/dL, and ≤ 70 mg/dL.
 - Percentage of time of specific ranges
 - Total count of specific ranges
 - Total hypoglycemia symptoms counted during specific ranges
- Plasma naloxone concentrations will be collected to model the pharmacokinetics and pharmacodynamics using a population modeling approach. This will be used to investigate dose levels and regimens for future studies.

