At 1 pm, the afternoon period of exercise will start and will be maintained as in the morning for a total of 2 hours. A third dose of 4.0 mg intranasal naloxone or the same volume of saline will be administered at the start of the afternoon exercise, and a final dose of 4.0 mg intranasal naloxone will be given 45 minutes after the start of the afternoon exercise. Blood samples for subsequent measurement of naloxone will be collected at 4-5 predetermined time points from each participant to allow subsequent population pharmacokinetic modeling. After completing the afternoon exercise, participants will be sent home with instruction on avoiding hypoglycemia and using the CGM. Before participants are sent home, a meal will be provided.

Part 1 Day 2: Participants will return the following day, and undergo a two-hour hyperinsulinemic (infusion of 2.0 mU/kg/min) hypoglycemic clamp in which blood glucose will be allowed to drop to 50 mg/dL. Symptom scores will be collected using a standardized questionnaire before and every 15 minutes during the hypoglycemic clamp study. Samples for later measurement of epinephrine, norepinephrine, glucagon and cortisol will be collected at baseline and every 15 minutes during the two-hour infusion period. After completing the clamp, participants will be

PROTOCOL TITLE: Hypoglycemia after exercise in type 1 diabetes: Intranasal naloxone as a novel therapy to preserve hypoglycemia counterregulation

VERSION 8 – December 7, 2018

given a meal and instructions for using the CGM for the next 7 days. At the completion of Part 1, participants will be scheduled to return to complete part two to receive the alternate therapy.

Wash-out Period: For a total of approximately 7 weeks, participants will be instructed to continue with all normal activities.

Seven days before scheduled Part 2 Visit: Participants will be asked to come in for a visit to apply the CGM. Application of the sensor and instructions are as above.

Part 2 Day 1 and Part 2 Day 2: The second part of the study will follow exactly as above with the exception that the participant will receive the alternate therapy to complete the cross-over. Those who received naloxone in Part 1 will receive saline in Part 2, and vice versa.

A mid-point A1C may be collected at this visit. A clinical A1C from the medical record can be used if within three months of the Screening A1C.

5.3 Follow-Up:

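### Does Aim 1 fail for want of one named symptom-score value per clamp and a definition of complete data?

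*Combined protocol and SAP*

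**What the plan says.** Section 3.1 sets the Aim 1 outcome as the naloxone-versus-saline difference "in symptom scores collected using a standard questionnaire during the hypoglycemic clamp on Day 2", and Section 16.2 repeats this. Section 16.1 words it differently: "The Aim 1 primary outcome is difference in symptom scores collected during hypoglycemia on day 2". The definitions list has "Hypoglycemia: low blood glucose (<60 mg/dL" as the threshold, and Section 5.2 describes a two-hour "hypoglycemic clamp in which blood glucose will be allowed to drop to 50 mg/dL". On timing, Section 5.2 says: "Symptom scores will be collected using a standardized questionnaire before and every 15 minutes during the hypoglycemic clamp study".

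For Aim 2 the value is named: "peak epinephrine during the hypoglycemic clamp on day 2 of each part", giving two observations per participant. The model in Section 16.1 has fixed effects for treatment, order and period and a random participant effect. It has no term for time within the clamp.

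The analysis set is defined by this sentence: "All randomized subjects who have complete outcome data for one or both of parts 1 and 2 will be included in the analysis". Section 14.1 allows a session to be stopped "due to technical malfunction or study MD/PA feels that it is no longer safe for the participant to continue".

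Section 16.2 bases the sample size on an SD of paired differences of 12.9 points, taken from an earlier naltrexone study, and a difference of 7.53 points with 25 completers.

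**The concern.** Three things look wrong on a first reading.

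- **Window.** Read literally with the 60 mg/dL threshold, scores taken during hypoglycemia are a subset of scores taken during the clamp, because glucose is still falling at the start. The two sections would then define the first primary outcome on different readings.
- **Value.** Aim 2 is a peak. Aim 1 has about eight on-clamp scores and a model that takes one, and no rule connects them.
- **Completeness.** A clamp stopped early has a peak up to the stop, but no final score and not the full set. Whether that part enters the analysis depends on a definition the plan does not give.

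If all this held at full strength, two analysts could follow the text and use different readings and different participants. An all-clamp mean could dilute the difference with scores from the glucose descent. If stops went with strong symptoms, the parts left out would be the high-scoring ones. Under Hypothesis 1 these would more often be naloxone parts, and the estimate would shrink.

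**Working it through.** **1. The plan's own figure.** Inputs from Section 16.2: difference 7.53, SD of paired differences 12.9, n = 25, alpha 0.05 (sidedness not stated; two-sided assumed). For a paired t-test the noncentrality is 7.53/12.9 × √25 = 0.5837 × 5 = 2.919, on 24 degrees of freedom with critical value 2.064. Power is 79.96%. The difference detectable with 80% power is 7.534, against 7.53 stated. The figure reproduces.

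**2. Are there two windows?** Section 16.2 reports the pilot symptom results as coming from hypoglycemia carried out on Day 2, so the word there names the procedure, which is the clamp. The same section describes the Aim 2 outcome once as a peak measured during the clamp and once as secretion induced by hypoglycemia. Section 1.1 writes both aims in terms of hypoglycemia-induced responses. The document uses the two terms interchangeably.

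**3. When would the window matter?** For a peak or a last score, readings from the descent will rarely count. They matter for a mean or an area over the whole clamp, which no section proposes. To see the size, assume that k of 8 on-clamp scores precede 60 mg/dL and carry no effect. The difference becomes 7.53 × (8 − k)/8. Power is for 25 completers.

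| k | Difference | Power, SD stays 12.9 | Power, half the variance scales by ((8 − k)/8)² | Power, SD shrinks in proportion |
|---|---|---|---|---|
| 1 | 6.59 | 69% | 74% (SD 12.12) | 80% |
| 2 | 5.65 | 56% | 66% (SD 11.40) | 80% |
| 3 | 4.71 | 42% | 56% (SD 10.76) | 80% |

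The range runs from a large loss to none. The documents fix neither k nor how the SD behaves, so the table describes one assumed choice of summary and not the plan as written.

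**4. Completeness.** Assume each clamp is stopped and left out with probability q, unrelated to symptoms. A participant keeps both parts with probability (1 − q)². Power is the paired-t power averaged over the binomial number of complete pairs.

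| q | 25 starting: pairs, power | 30 enrolled: pairs, power |
|---|---|---|
| 5% | 22.6, 75% | 27.1, 83% |
| 10% | 20.2, 70% | 24.3, 78% |

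Twenty-five is the number of completers, so taking stopped clamps from it counts the loss twice. Sections 11.1 and 16.2 enrol about 30 to allow for loss, and Section 13.2 replaces withdrawn participants. The right-hand column is an upper bound, because the same margin must also cover screen failures and drop-out.

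**5. Bias from stopping.** Simulation of the planned mixed model with 25 participants (between-participant share of variance assumed 0.3 to 0.7) gives 5.7 to 6.3 points and 58 to 62% power if exactly the highest-scoring 10% of clamps are removed. If the tendency to stop correlates 0.5 with the score, the estimate is 7.1 to 7.2 points, close to 7.53. Sections 14.1 and 18.2 name monitoring failure and clinician safety judgement as grounds for stopping. Neither names a symptom score.

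**The case for a change.** The strongest argument for a change is that Aim 1 is the first primary outcome and drives the sample size, yet its value per part is not stated while the one for Aim 2 is. A literal reader cannot tell whether to use a raw score or a change from the pre-clamp score. Section 16.2 also does not say which summary the 12.9-point SD describes. If the analysed summary had SD 13.9, power with 25 completers would be 74%; at SD 14.9 it would be 68%. Section 13.3 keeps data from early terminators without saying whether a partial clamp is complete. Writing the definition down would cost almost nothing, since scores and glucose are already collected.

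The omission itself stands. It does not show a wrong result. The larger SDs are assumed, and a different summary could as well have a smaller one: at SD 11, power would be 91%. A clamp with all its scores, or with none, can be classified without help. Writing the definition down would mean choosing among acceptable summaries, not replacing a poor stated method with a better one. A peak taken up to an early stop has its own weakness, because it may understate the two-hour peak.

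**Conclusion.** No change to the plan follows. This is missing detail of a kind a competent analyst fills: one value per part, most obviously the peak to match Aim 2 or the mean during hypoglycemia, with a stated rule for partly scored clamps. Either choice fits the model in Section 16.1 and gives a valid treatment comparison. The two-window reading is loose wording, and the completeness rule is open only for partial clamps.

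The stated 25 completers and 80% power are right on their own inputs. The plausible cost of losing whole clamps at random is small: 78% power at an assumed 10% loss from 30 enrolled, as an upper bound, and 83% at 5%. The dilution and selective-stopping figures are illustrations under assumptions that the documents neither state nor imply.

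The conclusion rests on two assumptions: the summary is settled before unblinded data are seen, and partly scored clamps are uncommon. If the summary were picked after seeing treatment differences, the concern would become a real one about selective choice of outcome.
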